9.2.2. Method of Detecting AEs and SAEs

- The method of recording, evaluating, and assessing causality of AEs and SAEs and the procedures for completing and transmitting SAE reports are provided in [Appendix 3](#).
- Care will be taken not to introduce bias when detecting AE and/or SAE. Open-ended and non-leading verbal questioning of the participant is the preferred method to inquire about AE occurrence.

9.2.3. Follow-up of AEs and SAEs

After the initial AE/SAE report, the investigator is required to proactively follow each participant at subsequent visits/contacts. All AE/SAEs will be followed until the event is resolved, stabilized, otherwise explained, or the participant is lost to follow-up (as

defined in Section 8.5). Further information on follow-up procedures is given in [Appendix 3](#).

9.2.4. Regulatory Reporting Requirements for SAEs

- Prompt notification by the investigator to the sponsor of a SAE is essential so that legal obligations and ethical responsibilities towards the safety of participants and the safety of a study intervention under clinical investigation are met.
- The sponsor has a legal responsibility to notify both the local regulatory authority and other regulatory agencies about the safety of a study intervention under clinical investigation. The sponsor will comply with country-specific regulatory requirements relating to safety reporting to the regulatory authority, Institutional Review Boards (IRB)/Independent Ethics Committees (IEC), and investigators.
- Investigator safety reports must be prepared for suspected unexpected serious adverse reactions (SUSAR) according to local regulatory requirements and sponsor policy and forwarded to investigators as necessary.
- An investigator who receives an investigator safety report describing a SAE or other specific safety information e.g., summary or listing of SAE) from the sponsor will review and then file it along with the IB and will notify the IRB/IEC, if appropriate according to local requirements.

9.3. Treatment of Overdose

For this study, any dose of GSK2831781 greater than the agreed dose level will be considered an overdose.

GSK does not recommend specific treatment for an overdose.

If an overdose is identified by unblinded staff, but is less than 450 mg, this should be documented by the unblinded monitor (including the quantity of the overdosing), but no additional action need be taken.

If the total dose administered has exceeded 450 mg, investigators should:

1. Contact the Medical Monitor immediately.
2. Closely monitor the participant for AE/SAE and laboratory abnormalities for at least 4 weeks from the date the overdose occurred, and thereafter as advised by the Medical Monitor.
3. Document the quantity of the excess dose.

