7.1. Study Intervention(s) Administered

| Intervention Name | GSK2831781 | Placebo |
|---------------------------------------|--|--|
| Type | Biologic | N/A |
| Dose Formulation | GSK2831781, CCI [REDACTED] | Commercial saline solution, 0.9% (w/v) |
| Unit Dose Strength(s) | 150 mg/mL | N/A |
| Dosage Level(s) | IV: 450 mg SC: 150 mg or 450 mg | N/A |
| Route(s) of Administration | IV infusion or SC injection | IV infusion or SC injection |
| IMP and NIMP | IMP | IMP |
| Sourcing | Provided centrally by the Sponsor or designee | Supplied by site |
| Packaging and Labelling | Study intervention will be provided in vial. Each vial will be labelled as required per country requirement. | N/A |
| [Current/Former Name(s) or Alias(es)] | aLAG3, anti-LAG3 | N/A |

GSK2831781 is a fully humanized monoclonal antibody and all formulation ingredients have been previously used in the clinic.

Intravenous GSK2831781 (or placebo) will be diluted in 0.9% saline as described in the Study Reference Manual (SRM), and administered over a 2 hour infusion, with active post-dose monitoring for a further 2 hours. Participants will remain resident for a minimum of 24 following IMP administration.

SC GSK2831781 is administered as multiples of 150 mg injections, each provided as 1 mL of GSK2831781 150 mg/mL. Participants randomised to the different dose levels will receive:

- 450 mg dose level: 3x 150 mg GSK2831781.
- 150 mg dose level: 1x 150 mg GSK2831781 and 2x 1 mL 0.9% (w/v) saline for injection.
- Placebo: 3x 1 mL 0.9% (w/v) saline for injection.

Each participant in Part B will therefore receive 3 injections at the dosing visit. In an individual participant, injections should preferably be administered into the same part of the body (arms, legs or abdomen, either on the left or right side or both), but should be separated by a minimum of 2 cm. Syringes will be labelled in a blinded fashion, and the location of each injection will be recorded, so that the locations of active and placebo injections at 150 mg dose level are traceable. This is relevant for assessment of those

participants who receive both active and placebo injections.

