8.3. Role of the Safety Review Team (SRT)

An SRT will oversee the safety of participants in this study. The SRT will review blinded safety data at planned interims during the study, and unscheduled as required. Further details of the SRT are described in Section 11.1.5 and the SRT charter.

Unscheduled SRT reviews may be triggered as described in Section 8.2, if moderate or severe AEs are consistently observed across participants in a cohort or strata, or if unacceptable pharmacological effects reasonably attributable to GSK2831781 are observed. Should an unscheduled SRT review of this study be required, possible outcomes may include:

- Restart dosing at the current dose levels.
- Restart dosing but reduce the dose levels in Part A and/or Part B as guided by emerging safety data and data on GSK2831781 plasma concentrations.
- Stop dosing in the relevant part of the study (A or B) but continue with the other part.
- Stop dosing both Part A and Part B.

If the study is halted due to safety concerns based on a decision by the SRT (or DRC; see [11.1.5](#)), and a subsequent decision is made to restart dosing, this will only occur after competent authority authorization via a substantial amendment.

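### The overdose rule in protocol 9.3 states no action for a total of exactly 450 mg, and its fixed 450 mg cut-off does not follow the agreed dose level if the dose is reduced

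*Protocol*

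**What the plan says.** Protocol 9.3 opens with a definition tied to assignment: "any dose of GSK2831781 greater than the agreed dose level will be considered an overdose". Two action rules follow, both using a fixed figure.

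- The first begins "If an overdose is identified by unblinded staff, but is less than 450 mg". The unblinded monitor records the event and its size, and nothing further is required.
- The second begins "If the total dose administered has exceeded 450 mg, investigators should". It requires immediate contact with the Medical Monitor, close monitoring for at least 4 weeks, and a record of the excess.

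Protocol 7.1 fixes the possible subcutaneous totals: "SC GSK2831781 is administered as multiples of 150 mg injections, each provided as 1 mL of GSK2831781 150 mg/mL". Each Part B participant receives three injections, made up by arm as "450 mg dose level: 3x 150 mg GSK2831781", "150 mg dose level: 1x 150 mg GSK2831781 and 2x 1 mL 0.9% (w/v) saline for injection" or "Placebo: 3x 1 mL 0.9% (w/v) saline for injection". In Part A the choice is 450 mg IV or saline (7.1, 7.3).

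The dose level can change. Section 5.1 provides for randomisation to a lower level in Part A, 5.2 allows extra enrolment in both parts for this purpose, and 7.7 permits reduction after review by the Safety Review Team (SRT). One of the review outcomes in 8.3 is "Restart dosing but reduce the dose levels in Part A and/or Part B as guided by emerging safety data".

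**The concern.** Both conditions in 9.3 are strict inequalities on either side of 450 mg, and neither includes 450 mg itself. That value is not an unlikely boundary case. It is the amount a participant receives if a lower-dose or placebo allocation in Part B is wholly replaced by active syringes, or if a Part A placebo participant is given the active infusion.

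The definition and the actions also rest on different references. The definition moves with the agreed dose level; the cut-off does not. After a dose reduction, 450 mg would be the level that had been given up, yet it would still be the boundary for action, and a participant dosed at that level would have no action stated.

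What is at stake is a safety instruction that is silent when it is needed. The two rules also name different people, the unblinded monitor in one and the investigators in the other. An event that meets neither condition is therefore assigned to nobody, in a study where 7.4 keeps all staff blinded except the pharmacists or their delegates.

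**Working it through.** **Inputs.** Strength and volume per active syringe: 150 mg/mL and 1 mL (7.1). Syringes per Part B participant: three (7.1). Planned active syringes: three, one or none, for 450 mg, 150 mg and placebo (7.1). Part A active dose: 450 mg IV (7.1, 7.3). Let A be the agreed dose and T the total given. Section 9.3 then reads: overdose if T > A; record only if T < 450; escalate if T > 450.

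**Step 1: reproduce the plan's figure.** 1 mL × 150 mg/mL = 150 mg per syringe, and 3 × 150 = 450 mg. This matches the 450 mg dose level in 7.1.

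**Step 2: list every Part B syringe error that counts as an overdose.**

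| Assigned | Active syringes given | T (mg) | Excess T − A (mg) | T < 450? | T > 450? | Action in 9.3 |
|---|---|---|---|---|---|---|
| 150 mg | 2 | 300 | 150 | yes | no | record only |
| 150 mg | 3 | 450 | 300 | no | no | none stated |
| Placebo | 1 | 150 | 150 | yes | no | record only |
| Placebo | 2 | 300 | 300 | yes | no | record only |
| Placebo | 3 | 450 | 450 | no | no | none stated |

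Two of the five outcomes have no action. For a participant assigned 450 mg, three active syringes are the planned dose and not an overdose.

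**Step 3: can a syringe error reach the second rule?** The largest possible total is 3 × 150 = 450 mg, and the second rule needs T > 450. A mix-up among three syringes therefore never triggers it.

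**Step 4: Part A.** A placebo participant given the full active infusion has A = 0 and T = 450. This is an overdose with no stated action.

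**Step 5: after a dose reduction.** Let the new agreed level be any D < 450 mg.

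- D < T < 450: overdose, record only.
- T = 450: overdose, no stated action.
- T > 450: escalate.

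The pattern is the same for every D below 450 mg.

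**Step 6: the other reading of the first rule.** The first rule does not use the word total. If it is read as the excess, the 150 mg participant given 450 mg (excess 300) moves into record only, and so does a participant at a reduced level D above zero who is given 450 mg. The placebo participant given 450 mg (excess 450) is still in neither rule, in both parts. A participant assigned 450 mg and given, for illustration, 500 mg (excess 50) would fall under both rules, whose actions conflict. Neither reading gives exactly one action for every case.

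**The case against.** The strongest reply is that the gap sits at a dose the study plans to give. Eight Part B participants are meant to receive 450 mg SC, and 5.7 reports an average of 472 mg in the highest cohort of the earlier IV study. Escalating only above the highest planned dose is a coherent choice. A participant given 450 mg in error still has the scheduled laboratory tests, vital signs and adverse event collection through Day 112, and section 9 provides for Medical Monitor discussion of immediate safety concerns. A second staff member confirms dose and identity at dosing (7.5), and the safety analysis follows the intervention actually received (10.3). All of this stands, and it limits the immediate harm.

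On dose reduction, 8.2.1 and 8.3 make a restart after a safety halt depend on a substantial amendment, and 9.3 could be revised then. This stands in part. Section 7.7 covers events that do not meet stopping criteria and allows reduction after SRT review without itself mentioning an amendment. Nothing in either route requires 9.3 to be revisited.

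Three stronger inferences are tempting, and the documents do not support them.

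- A reader might infer that recording alone is too weak for an overdose above a reduced level but below 450 mg. Section 9.3 does state one action there; whether it is sufficient is the sponsor's clinical judgement.
- A reader might infer that 12 of the 20 planned Part B participants (8 + 4) are affected. That counts everyone whose arm permits the error. Only a participant actually given three active syringes in error would be affected, and the documents give no error rate.
- A reader might treat total versus excess as a serious ambiguity. The total reading fits better: 9.3 defines the overdose as the dose itself, names the total in the second rule, and refers to the excess separately.

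**Conclusion.** The point holds as a defect in a safety instruction. A total of exactly 450 mg has no stated action, although it is an overdose for anyone whose agreed dose is lower. It is the end point of two of the five Part B syringe errors that count as overdoses, and of a placebo-to-active error in Part A. The five outcomes are logical possibilities with no probabilities attached. The cut-off also stops matching the dose level in force once the dose is reduced, and the former 450 mg level then falls in the gap.

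The size is moderate. While 450 mg remains a planned dose, what is missing is mainly the named responsibility, the decision on contacting the Medical Monitor, and any monitoring beyond the schedule. The documents do not support saying that the rule fails in the cases where it matters most. The dose-reduction case needs two contingencies, a reduction and then an overdose, but the protocol provides for the first.

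The conclusion rests on reading the first rule as the total dose. Under the excess reading the gap narrows to placebo participants given 450 mg, and the two rules overlap elsewhere.

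**What to change.** Reconcile the two rules in 9.3 with each other, with 9.3's own definition of overdose, and with 7.1, 7.7 and 8.3. Every overdose total, including exactly 450 mg and any overdose after a dose reduction, should fall under exactly one stated action with a named person responsible. Express both rules as the total dose administered, so that the first cannot be read as the excess. Which cut-off and which action apply is for the sponsor to decide on clinical grounds; this point proposes neither.

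The cost is two or three sentences in 9.3, with no change to data collection.

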9.4. Pharmacokinetics

Blood (3 mL per time point) will be collected into K2-ethylenediaminetetraacetic acid (EDTA) tubes and processed to obtain plasma for PK analysis of GSK2831781 at the time points indicated in Section 2, SoA Tables. The actual date and time (24-hour clock time) of each blood sample collection will be recorded.

Details of blood sample collection, processing, storage and shipping procedures are provided in the SRM.

Drug concentration information that would unblind the study will not be reported to investigative sites or blinded personnel until the study has been unblinded.

9.4.1. Soluble LAG3 (sLAG3)

Venous blood samples will be collected for measurement of sLAG3 as specified in the Section 2, SoA.

9.5. Pharmacodynamics

The PD effect of GSK2831781 on LAG3⁺ target engagement and cell depletion will be determined through analysis of blood. Blood PD analysis will be undertaken through flow cytometry as specified in the Section 2 SoA.

More detailed immunophenotyping, including identification of regulatory T cells, may be carried out on samples from a subset of participants.

9.6. Genetics

A 6 mL blood sample for DNA isolation will be collected from participants who have consented to participate in the genetics analysis component of the study. Participation is optional. Participants who do not wish to participate in the genetic research may still participate in the study.

In the event of DNA extraction failure, a replacement genetic blood sample may be requested from the participant. Signed informed consent will be required to obtain a replacement sample unless it was included in the original consent.

See [Appendix 4](#), Section 11.4 for Information regarding genetic research.

9.7. Immunogenicity Assessments

Antibodies to GSK2831781 will be evaluated in serum samples collected from all participants according to Section 2, SoA. The detection and characterization of antibodies to GSK2831781 will be performed using a validated assay method by or under the supervision of the Sponsor.

Serum samples will be assessed for the presence of ADA using a tiered approach. Samples will first be screened for antibodies binding to GSK2831781. Samples with screening result above the screening cut point will be further assayed in an assay to confirm the specificity of the ADA. Samples testing positive in the confirmation assay will be further assayed through sequential dilution in order to report a titre value. The titre is the reciprocal of the last dilution at which the sample tests positive in the screening assay. Additional analysis may be performed on samples collected to monitor immunogenicity to assess the presence of neutralizing antibodies to GSK2831781 and/or to further characterize the immunogenicity of GSK2831781.

10. STATISTICAL CONSIDERATIONS

10.1. Statistical Hypotheses

The primary objective is to determine the safety and tolerability of single IV doses of GSK2831781 in healthy Japanese and Caucasian participants (Part A); or of single SC doses of GSK2831781 in healthy Caucasian participants (Part B). There are no formal hypotheses planned.

10.2. Sample Size Determination

10.2.1. Part A

There will be a minimum of 8 Japanese and 8 Caucasian participants in Part A. The participants in each ethnicity stratum will be randomised 6:2 to GSK2831781 (450 mg) or placebo.

If 0/6 of a particular safety event is observed among the GSK2831781 participants of an ethnicity stratum, then the upper limit of the exact 95% Confidence Interval indicates that a true incidence rate of 41.0% could not be ruled out. Using a Bayesian approach to determine the credible interval around an observed safety event, we will assume a flat Beta (1,1) prior. If in an ethnicity stratum we were to observe 1 safety event out of the 6 participants who received GSK2831781, then the posterior distribution would be Beta (2,6). In that case there is a 95% certainty that the true probability of the safety event lies between 0.04 and 0.58.

The following between-subject coefficients of variation (CV_b) for the geometric means of PK parameters were observed in the FTIH study 200630 following GSK2831781 IV administration:

| Study 200630 Volunteer type | Treatment group | CV_b (%) | |
|--------------------------------|-----------------|------------|------|
| | | AUC (0-t) | Cmax |
| Healthy volunteer | 0.0075 mg/kg | 32.0 | 19.1 |
| Healthy volunteer | 0.04 mg/kg | 27.3 | 25.6 |
| Healthy volunteer | 0.15 mg/kg | 36.8 | 18.3 |
| Psoriasis patient | 0.5 mg/kg | 34.2 | 23.5 |
| Psoriasis patient | 1.5 mg/kg | 13.8 | 15.5 |
| Psoriasis patient | 5 mg/kg | 24.2 | 22.2 |

The 5 mg/kg dose corresponds to an average of 472 mg; therefore, the corresponding CV_b %'s are a good approximation for 450 mg.

Assuming a sample size of 6, it is estimated that the lower and upper bounds of the 90% confidence interval for the geometric means of area under the curve (AUC) and Cmax will be within approximately 21.7% and 19.8% of the point estimate respectively.

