10.2.2. Part B

There will be a minimum of 20 participants in Part B, randomised 8:8:4 to low dose GSK2831781 (150 mg) or high dose GSK2831781 (450 mg) or placebo.

If 0/8 of a particular safety event is observed among the GSK2831781 participants, then the upper limit of the exact 95% Confidence Interval indicates that a true incidence rate of 33.6% could not be ruled out. Using a Bayesian approach to determine the credible interval around an observed safety event, we will assume a flat Beta (1,1) prior. If on GSK2831781 we were to observe 1 safety event out of the 8 participants, then the posterior distribution would be Beta (2,8). In that case there is a 95% certainty that the true probability of the safety event lies between 0.03 and 0.48.

To date we do not have any GSK2831781 SC PK variability data available. Therefore, literature data was used to obtain informative priors for the absorption rate constant (k_a) and bioavailability (F). Using these priors, and the PK/PD relationship derived from the data of the First Time in Humans Study 200630, a sample size of 8 participants on active treatment has a probability of 65% to result in a median cell depletion in blood greater than 90% at week 4 after dosing.

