10.2.3. Sample Size Sensitivity

A sample size sensitivity analysis was conducted to investigate different safety event rates. A Bayesian approach was used, specifying a flat Beta (1,1) prior. If the number of subjects who complete each active dose reduce, then the 95% credible interval of the true event rate would change:

| N Dosed | Number of a particular safety event observed with GSK2831781 | 95% certain that the true probability of the safety event lies between |
|---------|--|--|
| 8 | 2 | (0.07, 0.60) |
| | 3 | (0.14, 0.70) |
| 7 | 0 | (0.00, 0.37) |
| | 1 | (0.03, 0.53) |
| | 2 | (0.09, 0.65) |
| 6 | 2 | (0.10, 0.71) |
| | 3 | (0.18, 0.82) |
| 5 | 0 | (0.00, 0.46) |
| | 1 | (0.04, 0.64) |
| | 2 | (0.12, 0.78) |
| 4 | 0 | (0.01, 0.52) |
| | 1 | (0.05, 0.72) |
| | 2 | (0.15, 0.85) |

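### The zero-event limits of 41.0% (0/6) and 33.6% (0/8) in Protocol 10.2.1 and 10.2.2 are labelled exact 95% confidence limits but are flat-prior credible limits; the exact limits are 45.9% and 36.9%

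*Protocol*

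**What the plan says.** Protocol 10.2.1 sets the Part A allocation: "The participants in each ethnicity stratum will be randomised 6:2 to GSK2831781 (450 mg) or placebo". It then takes the case in which none of the six on active treatment has the event: "then the upper limit of the exact 95% Confidence Interval indicates that a true incidence rate of 41.0% could not be ruled out".

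Protocol 10.2.2 repeats the statement for an active dose group of eight in Part B, again with no events: "then the upper limit of the exact 95% Confidence Interval indicates that a true incidence rate of 33.6% could not be ruled out".

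In each section the next sentence moves to what reads as a separate, Bayesian calculation (in 10.2.1: "we will assume a flat Beta (1,1) prior") and applies it to a single observed event. The resulting intervals are 0.04 to 0.58 for 1/6 and 0.03 to 0.48 for 1/8.

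Protocol 10.2.3 tabulates further intervals for 4 to 8 participants dosed and names one method for all of them: "A Bayesian approach was used, specifying a flat Beta (1,1) prior". Its zero-event rows give upper limits of 0.52 (n = 4), 0.46 (n = 5) and 0.37 (n = 7). For n = 6 and n = 8 the table shows only two and three events, because the zero-event and one-event cases for those sizes are in the text of 10.2.1 and 10.2.2.

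The SAP provided neither restates nor corrects these figures.

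**The concern.** An exact 95% confidence limit for zero events has a simple closed form, and 41.0% and 33.6% do not satisfy it. Both are too low, which is the reassuring direction: as labelled, the text says that zero events exclude more than they do.

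Safety and tolerability is the primary objective and no formal hypothesis is planned (Protocol 10.1). Statements about what zero events can rule out are therefore part of how the protocol describes the information that groups of six and eight provide. They stand beside the one-event credible intervals, the PK precision for n = 6 and the depletion probability for n = 8. A reader who applies the named method will not obtain the printed numbers. A reader who trusts the label will also think that the zero-event figures in the text and those in the 10.2.3 table come from different methods, when they form one series.

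**Working it through.** **Inputs.** Zero events in n = 6 (10.2.1) and in n = 8 (10.2.2); 95% level; prior Beta(1,1) (10.2.1 to 10.2.3); printed limits 41.0% and 33.6%.

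**1. The method named.** The two-sided exact (Clopper-Pearson) upper limit U for 0/n solves (1 − U)^n = 0.025, so U = 1 − 0.025^(1/n).

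- n = 6: 1 − 0.025^(1/6) = 0.4593, or 45.9%, against 41.0% printed.
- n = 8: 1 − 0.025^(1/8) = 0.3694, or 36.9%, against 33.6% printed.

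Checking in the other direction: at a true rate of 41.0% the chance of 0/6 is 0.59^6 = 0.042, and at 33.6% the chance of 0/8 is 0.664^8 = 0.038. A two-sided exact limit would give 0.025 and a one-sided limit 0.05.

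**2. Other interval methods.** The one-sided exact bound, 1 − 0.05^(1/n), gives 39.3% and 31.2%. For 0/6 and 0/8 respectively, other methods give:

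- Blaker: 40.6% and 35.9%
- Sterne: 41.1% and 36.5%
- Wilson: 39.0% and 32.4%
- Agresti-Coull: 44.3% and 37.2%
- Jeffreys: 33.0% and 26.2%
- Rule of three: 50.0% and 37.5%

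None matches both printed figures. Sterne comes close for 0/6 but is 2.9 points away for 0/8 (36.5 − 33.6).

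**3. The flat prior.** With a Beta(1,1) prior, zero events in n give the posterior Beta(1, n + 1). Its 97.5th percentile is 1 − 0.025^(1/(n+1)).

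- n = 6: Beta(1,7), 1 − 0.025^(1/7) = 0.4096, or 41.0%. This is the printed figure.
- n = 8: Beta(1,9), 1 − 0.025^(1/9) = 0.3363, or 33.6%. This is the printed figure.

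**4. The zero-event series.**

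| n | Exact two-sided upper limit | Flat-prior upper limit | Printed | Where printed |
|---|---|---|---|---|
| 4 | 0.602 | 0.522 | 0.52 | 10.2.3 |
| 5 | 0.522 | 0.459 | 0.46 | 10.2.3 |
| 6 | 0.459 | 0.410 | 41.0% | 10.2.1 |
| 7 | 0.410 | 0.369 | 0.37 | 10.2.3 |
| 8 | 0.369 | 0.336 | 33.6% | 10.2.2 |

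All five printed values follow the flat-prior column. The two in the text fill the gaps that the table leaves.

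**5. The remaining intervals.** The two one-event intervals in the text reproduce: Beta(2,6) gives 0.037 to 0.579 (printed 0.04 to 0.58) and Beta(2,8) gives 0.028 to 0.482 (printed 0.03 to 0.48). All 13 rows of the 10.2.3 table also reproduce to two decimals under Beta(1 + x, 1 + n − x). The row for 0/4 is informative at its lower end: the flat prior gives 0.005, printed as 0.01, where an exact interval would give 0.

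**6. Size of the difference if the label is kept.** 45.9 − 41.0 = 4.9 points for 0/6, and 36.9 − 33.6 = 3.3 points for 0/8.

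**The case against.** The strongest reply is that little depends on these figures. Safety is summarised descriptively (Protocol 10.4.1; SAP section 8), the halting and review triggers in Protocol 8.2 are event-based, and neither limit feeds a sample size or a planned analysis. The message is also much the same either way: zero events in six or eight people exclude only high rates, whether the limit is 41% or 46%, or 34% or 37%. All of this stands, and it limits the weight of the point.

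Second, a reader can recover the figures, because the prior that produces them is in the next sentence and the table uses the same method. That is fair. What fails is reproduction by the method named.

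Third, how the figures arose is inferred. Since 1 − 0.025^(1/(n+1)) is also the exact limit for 0/(n + 1), the printed values equal the exact limits for 0/7 and 0/9. No group of nine appears in section 10.2, and the table fits the flat-prior reading far better. Still, the protocol does not say how the numbers were produced, and the authors may have intended a frequentist statement for zero events. In that case the numbers should change, not the label. This is a reason to offer both repairs. It does not make the current text correct.

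**Conclusion.** The concern holds. In two places the named method and the printed number disagree. If the label is taken at its word, the limits should be 45.9% and 36.9%, so the text is 4.9 and 3.3 percentage points too low. If the numbers are taken as intended, there is no numerical error and only the description is wrong. The second reading is the more likely, because all 15 other event-rate intervals in 10.2.1 to 10.2.3 (two in the text and 13 in the table) follow the flat prior.

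The conclusion takes exact 95% interval in its usual sense, a two-sided Clopper-Pearson interval, but it does not depend on that choice: no exact variant tried, one-sided or two-sided, gives both printed values. The text should be corrected because it describes precision on the primary objective. The design and the analysis are unaffected.

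**What to change.** Preferred: in 10.2.1 and 10.2.2 keep 41.0% and 33.6%, describe each as the upper limit of a 95% credible interval under a flat Beta(1,1) prior, and move the sentence introducing the prior ahead of the zero-event statement. The whole of 10.2.1 to 10.2.3 then uses one method for event rates.

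Alternative, if a frequentist statement was intended: keep the exact-interval label, print 45.9% and 36.9%, and add a note that these are not comparable with the 10.2.3 table. Without the note, exact 0/6 (45.9%) and exact 0/8 (36.9%) would coincide with the table's flat-prior entries for 0/5 (0.46) and 0/7 (0.37), as though losing a participant cost no precision.

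The cost is one phrase and a reordered sentence in two places, or two numbers and a note. Design, sample size and analysis do not change.
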